Purpose. The purpose of this pilot study is to examine intervention feasibility and acceptability and determine effective recruitment and retention strategies, randomization processes, participant tracking and follow-up procedures, retention benchmarks, and evaluate the feasibility of outcome measures. To this end, we will conduct this feasibility trial using a two-group randomized attention control trial design.

Intervention Delivery. Drs. [name] and [name] are certified teachers of existing youth-focused MBI curricula, *.b*⁸⁹ ([name], [name]), and *MBSR-T*¹⁰⁸ ([name]), and will work with the interventionist if issues arise during intervention delivery. Additionally a fidelity checklist will be made to assess the delivery of the tailored *.b*. While the session length, group size, and session spacing will be informed by the PDSA work with the HYWG and finalized in the formative phase, we describe our estimates below. We anticipate between 4 and 5 intervention sessions that will last between 60-90 minutes. Each cohort will include approximately 10-15 youth. Based on attendance at our recent pilot *.b* program, we plan to recruit 15 youth to have an average final group size of 10 youth depending on HYWG preferences and PDSA data. We anticipate having 6 cohorts of youth (3 intervention and 3 attention control). Each session will likely include brief didactic presentations, videos, and mindfulness practice followed by inquiry. We anticipate that sessions will take place twice a week. Sessions will be held on site at the CHT shelter in a quiet, designated learning space to ease access to sessions for the participants and to assure access to shelter staff (e.g., social workers and case managers) and services (e.g., food and shelter). CHT has onsite, weekday clinical and mental health care and established protocols for accessing needed resources 24/7. Selection criteria for the interventionist include maintaining a personal mindfulness

practice for at least two years, trained in .b, and prior experience working with high-risk youth. The interventionist will receive additional training in Trauma-Informed Care as well as study procedures.

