Enrollment and Data Collection Procedures. The RC and RA will recruit and enroll all participants. Once consented, the youth will take the baseline survey and receive their group assignment from the RC. A computerized randomization generator will be used. The RA will be blinded to group assignment and will conduct all data collection. For the purpose of this study, enrollment will be defined as completing consent, baseline survey, and at least one lesson of the intervention or control condition. Surveys will be completed by participants on iPads using REDCap. Participants will enter response data directly into the tablet so their answers will be private. In the case of electronic device failure, we will use back-up iPads and paper surveys and the RA will enter the responses into REDCap within 24 hours. We will use unique study IDs in the place of names to protect participant confidentiality. **Baseline and Follow-up Surveys.** Participating youth will complete surveys at baseline, immediate post-intervention, and at 3- and 6-months post-intervention. Surveys will take approximately 30 minutes to complete and will include items to measure mindfulness, perceived stress, emotion regulation, impulsivity, and mental health symptoms (see Table 2 for example measures and psychometric properties) and youth risk behaviors. We will also pilot self-report and app use to determine the most effective way to measure use of commercially available mindfulness apps. Data usage information will be gathered from mediation app on participants' phone. **Pre- and Post-Session Surveys.** Very brief pre- and post-session brief surveys will capture real-time stress, emotion regulation, positive and negative affect, mindfulness, impulsivity, and session feedback (post-session only) including likability of session content, delivery format, length, and delivery timeframe. These surveys will take approximately 5 minutes to complete prior to and immediately after each session. **Exit Interviews.** The RC will conduct individual or group exit interviews with 20 youth from the pilot study participants that will be audio-recorded and take about 30-45 minutes. We will randomly select participants from each of the 4-6 intervention cohorts to have equal representation by gender identity, age, and study group. We will elicit participant feedback on study procedures, intervention acceptability, delivery methods and strategies, barriers and facilitators of

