Data Management. The PI and Co-Is will be blinded to group assignment. The RA will download survey data from REDCap after each intervention session and store it directly onto a desktop computer encrypted master file. The RC will check data weekly for completeness. Survey and audio transcript data will be maintained in the Data Center Zone at UTHealth with data access limited to only necessary staff. Standard firewall and password protections will be implemented to limit access to and ensure confidentiality of data. To assure data security, we will make weekly backup copies of this master file onto an encrypted portable hard drive, which will be stored in the PI's office in a locked file cabinet. Unique logins will be assigned to each staff member. All data collected will be kept confidential and study IDs will be used in the place of participant names. A master list of study IDs linked to participant names will be maintained by the RC for the explicit purpose of linking participant data from baseline, follow-up, and pre- and post-intervention session surveys. This list will be stored in an encrypted, password-protected computer file. Only the RC and PI will have access to this file. Hard copy field notes, surveys, and participant contact information will be securely kept in a locked filing cabinet in a locked office by the PI. No personal identifying information will be recorded or labeled on field notes. All study-related forms, surveys, and data will be shredded after seven years. Confidentiality is a high priority and will be further protected with the Certificate of Confidentiality from NIH. A Data Safety and Monitoring Board (DSMB) will be included to manage the reporting and adjudication of unanticipated problems and serious adverse events to the IRB, NIH-NCCIH, and applicable regulatory agencies (See Form E. Human Subjects section). Results of this study will be reported in the aggregate.

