Pre-Post Session Survey Data. The brief pre-post session surveys will be finalized in YR-1. We anticipate measuring 'right now' measures of affect, stress, emotion regulation, and impulsivity, mindfulness, and mind wandering in the pre- and post-session surveys. We have used these items in our brief pilot of .b (manuscript under review). These brief surveys will take approximately five minutes to complete.

To assess the feasibility of proposed outcome measures we will pilot test them in the baseline and post-intervention surveys. While the surveys will be finalized during the development phase with the help of the HYWG and the Expert Advisory Panel, items will include those outlined in Table 2 and 3 in the Research Strategy.

Exit Interview. A subsample of approximately 20 participants will be asked to participate in a brief, semi-structured private or group exit interview to provide insight about the intervention and study

experience within two weeks of completing the pilot. We will randomly select and contact participants from each of the study arms ensuring that equal numbers of participants by group are selected. This will allow us to assess feasibility and acceptability of the intervention and the control condition and study procedures for all participants. The research staff, who will be trained in human subjects research methods, and trauma-informed qualitative research methods, will conduct the exit interviews using an open casual conversation style.

Example Exit Interview Guide. While the exit interview guide will be finalized during YR-1, we anticipate the RA will query the participants about: 1) what the participant thought of the number and types of questions asked in the baseline, pre-post session, and initial follow-up survey, 2) what they thought of the intervention sessions (e.g., content, length, delivery mode, frequency/spacing, perceived impact), 3) how useful the pre-programmed smartphone resource materials were (e.g., if they used it and for what), 4) utilization of smartphone apps to facilitate mindfulness practices, and 5) any other comments the participant has about the intervention or study procedures. Participants will receive a \$10 gift card for a local restaurant or grocery store for completing the exit interview.

Quality control and assurance

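### The research assistant is declared blinded but, as written, learns each attender's arm at the session surveys, so only the baseline survey can be collected blind

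*Combined protocol and SAP*

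**What the plan says.** All of the following is in the combined protocol and SAP, mostly under Specific Aim 3.

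- **Blinding and role.** Enrollment and Data Collection Procedures says: "The RA will be blinded to group assignment and will conduct all data collection".
- **Assignment.** The same section says: "Once consented, the youth will take the baseline survey and receive their group assignment from the RC". The RC therefore knows the arm, and the baseline survey comes before assignment.
- **Session surveys.** Still in that section: "Very brief pre- and post-session brief surveys will capture real-time stress", with other momentary measures. On timing: "These surveys will take approximately 5 minutes to complete prior to and immediately after each session". The post-session form adds "session feedback (post-session only) including likability of session content, delivery format, length, and delivery timeframe".
- **Single-arm classes.** Intervention Delivery plans six cohorts, three per arm, with 4 or 5 sessions of 60 to 90 minutes. Attention Control Condition describes a health-education programme whose instructor has a different background from the mindfulness interventionist.
- **Exit interviews.** Enrollment and Data Collection Procedures gives them to the RC. Under Data handling and record keeping, the Exit Interview paragraph gives them to research staff generally, and the Example Exit Interview Guide says "we anticipate the RA will query the participants about" a list of topics that includes the sessions.
- **Mode.** Participants enter their own survey answers on a tablet. If the devices fail, paper is used and the RA keys the answers.

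**The concern.** Blinding a data collector requires keeping that person away from anything that reveals the arm. Here the person named as blinded is also the only person named to collect data, and part of that collection takes place at the classes themselves. Someone who surveys a group as it enters and leaves a mindfulness class, or a health-education class, knows which arm the group is in. No section assigns the session surveys to other staff, separates a session data collector from a follow-up assessor, or says how the RA's blind is kept or checked.

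What is at stake is mainly the accuracy of the procedure. The pilot exists to try out trial methods for a larger randomized trial. If the blinding statement is carried forward as it stands, the later trial would inherit a safeguard that the pilot never had. A smaller stake is influence on the few data items that are not purely self-entered.

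**Working it through.** The plan gives no figure on this point to reproduce. The check is a comparison of sections plus a count.

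**Order of events for one participant**

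1. Consent, then baseline survey. Assignment has not yet been given, so the RA can be blind.
2. The RC gives the assignment. The RA can still be blind.
3. First class: a survey before and a survey after, the second asking about that class. The class is single-arm, so the RA who collects these surveys learns the arm.
4. Remaining classes: the same again.
5. Immediate post-intervention, 3-month and 6-month surveys: the RA already knows the arm.

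One attended class is enough. The section counts a youth as enrolled only after consent, the baseline survey and at least one lesson, so everyone who meets that definition has passed step 3. Youth who are assigned but never attend have not.

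**How often the arm is shown**

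Inputs: 4 or 5 sessions and 6 cohorts (Intervention Delivery); 2 surveys per session (Enrollment and Data Collection Procedures).

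- Session surveys per full attender = sessions × 2: 4 × 2 = 8, or 5 × 2 = 10.
- For a youth who just meets the adherence benchmark of 3 of 5 sessions (Table 3): 3 × 2 = 6.
- Class sessions = cohorts × sessions: 6 × 4 = 24, or 6 × 5 = 30.
- Group survey occasions = class sessions × 2: 24 × 2 = 48, or 30 × 2 = 60.

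All of these come before the first post-baseline assessment.

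**Where knowledge of the arm could matter**

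- Self-entered tablet scales: little room for the RA to influence answers.
- The 3- and 6-month face-to-face visits include a question about serious health events and overnight hospital stays (Adverse Event Reporting). No asker is named, so it falls to the RA under the sentence on all data collection.
- Literacy screening flags youth who may need extra help with the surveys (Inclusion Criteria for Youth Participants).
- The RA keys the paper back-up surveys.

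**Exit interviewer**

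One section names the RC, another names research staff, and the example guide names the RA. If the RA does interview, the talk about the sessions reveals the arm again, for about 20 youth. These passages must be reconciled, but the session surveys carry the point without them.

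**The case against.** The strongest reply is that the sentence on all data collection is not meant literally. The same section gives exit interviews to the RC, and nothing says who hands out the tablets at class. On that reading the plan has an unstated division of labour, and baseline blinding is intact in any case. The reference to RAs in the plural under Participant Discomfort could even mean a second assistant. It is true that baseline can be blind and that a division may have been intended. But the exit interviews are the only stated exception, and no section divides session and follow-up duties.

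The second reply is that little follows from it. The scales are self-entered, the analysis plan rules out inferential testing, and the Table 3 benchmarks are mostly counts and rates. This largely stands, and it limits the consequence. It does not make the blinding statement true.

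Several stronger inferences are tempting, and the documents do not support them:

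- **That the Stroop, balloon and delay-discounting tasks are staff-run and so open to assessor influence.** Table 2 lists them as possible measures and gives no mode of administration.
- **That all 90 assignments become known to the RA.** The plan recruits 90 so that at least 60 receive a condition. Youth who never attend are not revealed by session surveys.
- **That the data download breaks the blind.** Data Management says "The RA will download survey data from REDCap after each intervention session", but the data carry study IDs, only the RC and the principal investigator hold the link to names, and nothing says that the files show the arm.
- **That unblinded RA tracking distorts the retention comparison.** Pilot Participant Tracking, Retention, and Follow-up gives reminders, calls and scheduling to the RC, who knows the arm already.

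**Conclusion.** The concern holds, with a limited consequence. As written, the RA is unblinded for every participant who attends a surveyed class, before any post-baseline assessment. Only the baseline survey can be blind. The exposure is 8 to 10 session surveys per full attender over 24 to 30 classes, and a single attended class suffices.

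This rests on two readings: that the RA runs the session surveys, because the plan gives all data collection to the RA and names nobody else, and that classes are single-arm, which the plan states. If another person was meant to run the session surveys, the remedy is to say so.

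A reader might infer that the outcome scores are biased. The documents do not show that. With self-entry on a tablet, bias in the scales is probably small, and its size cannot be computed from the plan. What remains is the health-event query, help with surveys, paper entry, and a blinding claim that would be inaccurate if taken into the larger trial. It should be corrected, but it does not threaten the feasibility aims.

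**What to change.** Preferred change, in Enrollment and Data Collection Procedures:

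- Have the RC, who already gives out assignments, or other existing unblinded staff, run the pre- and post-session surveys and do all exit interviews.
- Give the same person the app-usage data. App Testing chooses apps separately for the two conditions, so usage records could also show the arm.
- Limit the RA to the baseline, immediate-post, 3- and 6-month assessments.
- Reconcile the exit-interviewer wording in Enrollment and Data Collection Procedures, Exit Interview and Example Exit Interview Guide.
- Optionally, have the RA record a guess of each participant's arm at follow-up, as a check on the blind.

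The cost is more than the roughly 10 minutes of survey time per class (2 × 5). The RC must be present at the start and again at the end of a 60- to 90-minute class, for 24 to 30 classes. The arms are to be matched on location and timing. If that means classes run in parallel, which the plan does not say, one RC cannot cover both and a second unblinded person is needed.

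If this cannot be staffed, delete the RA-blinding statement and describe the outcomes as self-administered with an unblinded data collector. That is a short text edit. Neither option changes the design or the sample size.

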1. Serious events include any event or condition that is life threatening, results in a hospitalization, cancer or a physical or cardiac event serious enough to require medical attention. These events may be:
 - a. Fatal
 - b. Life threatening
 - c. Permanently disabling
 - d. Required or prolonged hospitalization (Admission—not ER visit)
 - e. Overdose
 - f. Significant hazard to patient
2. Non-Serious events includes all other events.

In addition, follow-up face-to-face visits at 3 and 6 months will include a query of subjects on whether they had “any serious health events that caused them to seek medical attention within the past 3 months,” and if any of these resulted in “hospitalizations overnight.” Details of these events will be recorded. All adverse reactions noted by any of the team members will be immediately reported to the principal investigator, the UTHealth IRB, Data Safety and Monitoring Board, and NCCIH. All adverse events will be reviewed monthly by the research team and annually by the monitoring board. Also, in keeping with NIH guidelines, minority status and gender will be included in these reports to allow for detection of differential effects.

Data and Safety Monitoring Plan. This study is considered to constitute minimal psychological and physical risk and no legal or social risks. The risks are minimal since educational interventions generally promote good health, not endanger it. Our eligibility criteria are established to exclude individuals for whom the study procedures are not appropriate. We also will screen subjects directly using validated and reliable items for collecting information on co-morbidities such as unresolved serious mental illnesses or low literacy. Using this multi-gated approach, we should be able to effectively screen out any individuals for whom this intervention is contraindicated. All health-related occurrences will be recorded and regularly reviewed by the research staff.

A few potential minimal risks to subjects exist: breach of confidentiality or normal risks associated with having a phone. Breach of confidentiality is not believed to present any significant risk given the data protections described above. However, to mitigate this risk we have outlined steps we will take to protect confidentiality in the Human Subjects sections

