Risk to Human Subjects. While mindfulness strategies have been shown to have positive impacts on participants and have minimal associated risk, there is the possibility of risk. There are no physical risks associated with participation. The possible risk of psychological distress is related to the types of study questions asked in the surveys concerning past events, current circumstances, thoughts and feelings, sexual behaviors, and sexually transmitted infections. As well, the practices of mindfulness may add risk of distress as youth experience thoughts and feelings that arise during the process. For data collection, participants may find thinking about thoughts and feelings that arise or answering questions about these issues upsetting; these questions will be asked in as sensitive a manner as possible. We use ACASI computer-based surveys to allow participants to read and answer the questions privately and not have to hear them aloud or tell another person, which may reduce any possible distress associated with answering the questions. While participants will be assured that their participation will not affect health and social services being provided at any location, some participants may feel concerned about or pressured to be part of the study. We will assure participants at the beginning of each session that their participation is voluntary and that they can participate in all, part of, or none of the session and can withdraw from the study at any time for any reason without penalty. Another potential risk is the loss of confidentiality or disclosure of information or data about the participant. We have detailed below extensive measures to ensure confidentiality and decrease the risk for disclosure of private information. While there were no reported adverse reactions to participating in mindfulness interventions in the team's previous work, there is the potential of stress and negative reactions from the self-reflection that the practices may evoke.

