Participant Discomfort. Mindfulness practices, survey questions, and exit interviews might create awkwardness or discomfort. A potential risk in participating in the proposed research is becoming more aware of and/or reporting past events, current circumstances, thoughts and feelings, and risk behaviors that may make participants feel uneasy. Our experienced research staff will receive an additional 16 hours of training before initiating recruitment for this study to assure that all protocols and procedures are followed. Our staff have worked on several studies with homeless youth under the supervision of [name]. If new staff are hired during the study, they would receive a minimum of 40 hours of project training in addition to the university-level and Human Subjects training. Research staff will have ongoing supervision in how to handle awkwardness, embarrassment, or discomfort. Participants can choose whether to be in the study or not. They may withdraw at any time without consequences of any kind. They may also refuse to answer any questions they do not wish to answer and still remain in the study. It is possible that there may be occasions when study participants exhibit stronger and more serious signs of emotional distress; we may encounter individuals who express suicide intent, have psychiatric emergencies, or exhibit other indicators of acute distress. Research staff will be trained to identify signs of acute distress or suicidal ideation and trained how to respond to them. With respect to the assessments, we will emphasize to research staff that if a participant becomes upset, they should be offered the option of discontinuing without penalty (i.e., still receiving payment) or continuing at a later time after a break. Further, the computer-assisted survey administration limits participant exposure to potentially sensitive items. For example, participants who have not engaged in a certain risk behavior, such as substance use, are not exposed to more detailed questions about use. Participants will also be informed that they may skip any item that makes them feel uncomfortable. In the event of any acute emotional distress, research staff will remain with the participant until s/he is no longer distressed.

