The CHT shelter where the intervention sessions will be conducted has 24-hour staff trained in managing acute episodes of distress or even psychosis. We will follow the protocols of the shelter, who have over 30 years of experience with homeless youth. Additionally, the shelter has a fully functional Federally Qualified Healthcare Center on the premises with clinical psychologists and a psychiatrist on staff. Individuals who wish to pursue follow-up care will also be given a referral list specifically tailored to the individual's request. We will have prepared referral lists for perpetrators and victims of abuse as well as for other psychological problems. At the end of each assessment, all participants will be offered a list of relevant, local referrals. We will not be asking about suicidal ideation, so it is unlikely that we will have to deal with acute suicidal ideation. However, anyone having direct involvement with the participants will be fully trained by the PI in procedures for assessment and intervention in cases where suicidal ideation is expressed. Research staff will be instructed to immediately contact shelter staff to implement shelter protocols on suicidal ideation and to contact the PI and take appropriate clinical action in these circumstances to assure participant and staff safety including referral to another level of clinical care. As well, recruitment will take place in shelters and drop-in centers staffed by trained clinical social workers, case managers, and healthcare providers. RAs will be able to notify recruitment site staff and facilitate implementation of protocols for care in cases of acute distress. Experienced supervisors

and [name] will be available for immediate consultation in the event of encountering an unexpected acute psychological problem; and as part of their training, research staff will be made familiar with referral resources and procedures for local psychological, social service, and other emergency care needs.

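### The serious-event definition leaves events treated without admission unsettled, and the only scheduled adverse-event question neither names psychological events nor reaches back into the session period

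*Combined protocol and SAP*

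**What the plan says.** The definition stands in Data and Safety Monitoring, under Adverse Event Reporting. It opens: "Serious events include any event or condition that is life threatening, results in a hospitalization". It then adds "cancer or a physical or cardiac event serious enough to require medical attention". A lettered list follows, introduced as what such events may be. Item (d) is "Required or prolonged hospitalization (Admission—not ER visit", item (e) is overdose and item (f) is "Significant hazard to patient", which is not defined. Every other event is non-serious.

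The same section asks participants at the 3- and 6-month visits about "any serious health events that caused them to seek medical attention within the past 3 months", and whether any of these led to an overnight hospital stay. No other scheduled adverse-event question is described.

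On expected harm, Ethics (Risk to Human Subjects) states that participation carries no physical risk. It says that "the practices of mindfulness may add risk of distress as youth experience thoughts and feelings that arise during the process", and also lists distress from survey questions, felt pressure to take part, and loss of confidentiality. Participant Discomfort, under Protection Against Risks, adds that "we may encounter individuals who express suicide intent, have psychiatric emergencies, or exhibit other indicators of acute distress". The same discussion states: "We will not be asking about suicidal ideation".

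**The concern.** Two things look wrong. First, the defining sentence and its list set different thresholds for an event that needed care but not admission, so two people classifying in good faith could disagree. The label has consequences: Data Management gives the monitoring board the task of managing the reporting and adjudication of unanticipated problems and serious adverse events.

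Second, the safety data fit poorly with the harms that the protocol expects. The limb triggered by medical attention alone is limited to cancer, physical and cardiac events, in a study said to carry no physical risk. The one scheduled question looks for medically attended serious illness after the sessions have ended. The pilot is meant to inform a larger trial. A report of few or no serious events could then reflect how events were sought and labelled as much as what happened to trauma-exposed youth during mindfulness practice.

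**Working it through.** The plan gives no event rate or safety threshold to reproduce. The check sets the texts side by side and then does simple date arithmetic.

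**Classification under the definition as written**

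| Event | Defining sentence | Lettered list | Result |
|---|---|---|---|
| Injury treated in an emergency room, sent home | Serious, because it needed medical attention | Not under (d); under (f) only by judgement | Unsettled |
| Psychiatric crisis managed on site, in a clinic or in an emergency room, no admission | Reached only if life threatening | Only if life threatening, permanently disabling, an overdose, or judged to fall under (f) | Otherwise non-serious |
| Psychiatric admission or life-threatening self-harm | Serious | Serious | Serious |
| Distress with no medical care | Not reached unless life threatening | Under (f) only by judgement | Otherwise non-serious, if it becomes known |

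The first row shows the unsettled threshold. The second shows that a psychological event needing care without admission faces a higher bar than a physical one.

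**Reach of the scheduled question**

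Inputs:
- Number of sessions: about 5 (Proposed Intervention Description); 4 to 5 (Intervention Delivery).
- Spacing: twice a week, anticipated (Intervention Delivery).
- Follow-up visits: 3 and 6 months after the intervention (Enrollment and Data Collection Procedures).
- Look-back: 3 months (Adverse Event Reporting).

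Span from first to last session = (sessions − 1) / sessions per week:
- 5 sessions: (5 − 1) / 2 = 2 weeks.
- 4 sessions: (4 − 1) / 2 = 1.5 weeks.

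Window covered, in months after the last session:
- First question: 3 − 3 = 0, so months 0 to 3.
- Second question: 6 − 3 = 3, so months 3 to 6.

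Together the windows cover months 0 to 6. The sessions lie in the 1.5 to 2 weeks before month 0, so with visits on schedule the overlap is nil. An early first visit would reach a little way into the sessions, and a late one would leave a further gap after them. The immediate post-intervention survey falls at the right time, but no adverse-event question is attached to it.

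**What remains for the session period**

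The routes are a participant calling the study number or telling staff, or staff noticing symptoms. Both depend on someone coming forward or being observed.

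**The case against.** The strongest reply is that known events are not lost. Whatever is not serious is non-serious by definition. All reported events go into the log and are rated for attribution, and all adverse events are reviewed monthly by the team and annually by the board. Significant symptoms lead to mental-health referral and consultation with the board. Adverse reactions noted by the team go at once to the principal investigator, the IRB, the board and NCCIH. Under Data Security, breaking confidentiality over a suicide concern is reported to the IRB. Staff are trained to recognise acute distress and to act on expressed suicidal ideation. All of this stands. A reader might infer that psychological events have no place to be counted, and the documents do not support that.

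It can also be said that item (d) limits only the hospitalization criterion, and that the introduction to the list makes it illustrative. On that reading the injury in the first row is simply serious. The reading is reasonable, so this is an unresolved inconsistency and not a strict contradiction. But Adverse Event Reporting sends the team and board to the list for classification and does not rank it against the sentence.

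Third, most limbs are cause-neutral: life threatening, hospitalization, permanently disabling, overdose and significant hazard apply to mental as well as physical events. It would be wrong to call the whole definition one of physical illness. The restriction lies in the medical-attention limb alone.

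None of these replies meets the ascertainment point, because the logging and review routes start only once an event has been volunteered or noticed.

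**Conclusion.** The point holds as one of classification and ascertainment. The class of a physical event treated without admission is unsettled. A psychological event treated without admission is serious only under narrower or undefined criteria. The scheduled question does not elicit distress that received no medical care, and it misses the session period of about 1.5 to 2 weeks.

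The size cannot be given as a number of events or a rate, because the documents contain no event rates. A reader might convert one reclassified participant into a share of an arm, but that share would be the same for any event and says nothing about this definition.

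Two stronger readings should be set aside. Practice-related distress is not the only foreseen harm, since Risk to Human Subjects names several others. Nor do the documents make a momentary worsening on a post-session survey an adverse event. They give no threshold for one, so a safety table of such changes would be a matter of preference.

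The look-back result assumes the anticipated session spacing, visits held on schedule, and follow-up counted from the end of the intervention. Enrollment and Data Collection Procedures and the description of the board's role both count it that way. If the visits were counted from enrollment, the first window would take in most or all of the sessions. The restriction to medically attended serious health events would remain in either case.

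**What to change.** Three changes, none of which requires a particular seriousness threshold to be adopted here:

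1. In Adverse Event Reporting, the sponsor should reconcile the defining sentence with the lettered list, and state which governs, so that events treated without admission, physical or psychological, are classified one way. Item (f) should be defined in the same edit.
2. In the existing follow-up question, name mental-health crises or marked distress, whether or not medical care was sought. Make the first look-back cover the session period, for example by asking about the time since joining the study.
3. In the existing adverse event log, flag psychological events wherever they were managed, and tabulate them by arm for the board. The principal investigator and co-investigators are to be blinded to assignment, so the by-arm table belongs in the board's closed session.

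The cost is a wording change in one section, a phrase and a time frame in a question already asked, and one flag in a log already kept. The downside is somewhat more events to record and review.
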